10.4.3. Exploratory Indicator Analysis

Effect of CD24Fc on systemic steroid dosage: The frequency and dosage of glucocorticoids in all treatment groups will be collected to evaluate the potential impact of CD24Fc on steroid dosage.

Effect of CD24Fc on cytokine levels: monitoring during the treatment / observation period including C-reactive protein, IL-6, IL-1 β , IFN- γ , TNF- α , IP10, MCP, GCSF, IL10 and other cytokines and their risks. The level of dynamic changes of related model molecules (HMGB-1, HSP70 / 90), to assess the possible correlation between the levels of various cytokines and disease outcome and prognosis.

Effect of CD24Fc on the distribution of lymphocyte subtypes: monitor the dynamic changes of the proportion of CD4 and CD8 T cell subtypes in lymphocytes during the treatment /

observation period and analyze the state of T cell depletion, and evaluate the lymphocyte level and disease outcome and prognosis may be relevant.

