1.2. Rationale for Clinical Study of CD24Fc for COVID-19 Treatment

As the newest global medical emergency (9), COVID-19 exhibits features that are unlikely ameliorated solely by antiviral-based therapeutic approaches.

First, although the new coronavirus (SARS-CoV-2) viral load was reduced around day 9 after appearance of clinical symptoms in upper respiratory samples (13), radiology studies based on CT scan suggest that lung damage peaked after day 9 and lasted well beyond 14 days (3) (Figure 2a). The lung tissue in autopsy samples showed diffuse alveolar destruction and bronchiolar epithelial cell death. There are type II pneumocyte proliferation and interstitial infiltration of macrophages, some forming multi-nucleated giant cells similar to giant cell pneumonia. There are diffuse alveolar capillary congestion and alveolar disconnection and disintegration (14) (Figure 2b). This is reminiscent of findings in SARS-CoV infected patients where pneumonitis can peak after clearance of the virus (findings in SARS-CoV infected patients where pneumonitis can peak after clearance of the virus (15-17). Therefore, a successful countermeasure must include amelioration of lung inflammation by non-antivirals. In this context, it is of important to note that, since steroid, the anti-inflammatory drug widely used in addressing severe inflammation, was not recommended for COVID-19 or SARS (18, 19), new approach is urgently needed.

Figure 2: Radiological and histological presentation of COVID-19.

Second, patients with severe clinical symptoms show significant T cell lymphopenia that rivals human immunodeficiency virus (HIV) infection (Figure 3). In contrast, patients with mild clinical symptoms have largely normal lymphocyte counts (20). The reduction of lymphocytes is due to loss of CD4 and CD8 T lymphocyte as B cell numbers are unaffected (20). In addition, functional exhaustion of T cells is suggested by high expression of T-cell exhaustion markers (8). There were significant increase of several inflammatory cytokines in the serum (20) (Figure 4). The deletion and functional exhaustion of T cells prevent successful clearance of SARS-CoV2, therefore further delaying clinical recovery.

Figure 3: The absolute lymphocyte numbers and subtype lymphocyte numbers in mild and severe COVID-19 patients.

Severe COVID-19 patients have lymphopenia and reduced T lymphocyte numbers similar to HIV infection.

[figure not shown]
[figure not shown]

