We first investigated whether CD24Fc treatment influences HIV-1 replication and immunopathogenesis in acute HIV-1 infection with humanized mice. As shown in [Figure 7a](#), in the vehicle-treated group, R3A replication rapidly increased to 1×10^6 copies/mL at 1 week post-infection (wpi) and then it gradually increased to 10^8 copies/mL at 2-3 wpi. In the CD24Fc treated group, R3A increase in the first week was unaffected. However, no further increase was observed at 2 and 3 wpi. Nevertheless, CD24Fc treatment affected both CD4 and CD8 T cells equally as it did not reduce CD4 T cell frequency among CD3⁺ T cells ([Figure 7b](#)). Notably,

CD24Fc treatment significantly increased the numbers of CD4⁺ T cells in the spleen at the termination of the mice at 3 wpi (Figure 7c). This increase of CD4⁺ T cell number corresponded with an increase of the total human lymphocytes in the spleen of humanized mice (Figure 7d). These data indicate that CD24Fc has the potential to reduce HIV-1 viral load and protect T cells from depletion in the spleen of humanized mice with acute HIV infection. Since the CD4 and CD8 ratio was not altered (Figure 7b), CD24Fc protected against loss of both CD4 and CD8 T cells.

Figure 7: CD24Fc treatment reduces HIV-1 viral load and protects CD4⁺ T cells from depletion in the spleen of humanized mice with acute HIV infection.

(a) The effect of CD24Fc treatment on plasma HIV-1 loads in of R3A infected mice with or without CD24Fc administered by i.p. at 5 mg/kg on days 1, 8 and 15 after infection. (b) Summary data of the percentages of CD4⁺ T cells in the peripheral blood of R3A infected mice with or without CD24Fc. (c and d) Summary data of the absolute number of CD4⁺ T cells (c) and total human lymphocytes (d) in the spleen of R3A infected mice with or without CD24Fc at termination. Data shown are mean and s.e.m. *P < 0.05, ** P < 0.01 (analysis of two-tailed unpaired Student's t-test). Similar protection of CD8 T cells are achieved as the CD4% in T cells was unaffected by CD24Fc.

[figure not shown]
We have recently reported that CD24Fc protected Chinese rhesus monkey against SIV-induced AIDS and death, primarily by reducing organ damage caused by inflammation (18). To test

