7.1.5. Laboratory tests

Blood tests: red blood cell count (RBC), hemoglobin concentration (HGB), white blood cell count (WBC), platelet count (PLT), neutrophil count (ANC), lymphocyte count (LY), monocyte count (MO), Eosinophil count (EO), basophil count (BA).

Blood biochemical tests: aspartate aminotransferase (AST), alanine aminotransferase (ALT), alkaline phosphatase (ALP), γ -glutamyl transpeptidase (γ -GT), albumin (ALB), total bilirubin (TBIL), direct bilirubin (DBIL), lactate dehydrogenase (LDH), urea nitrogen (BUN) / urea (Urea), creatinine (Cr), creatine kinase (CK), creatine kinase isoenzyme (CK -MB), fasting blood glucose and cardiac Troponin I.

C-reactive protein (CRP), ESR.

Urine routine examination: urine pH, urine red blood cells, urine white blood cells, urine protein, urine glucose, urine ketone body.

Examination of coagulation function: D-dimer, prothrombin time (PT), activated partial thromboplastin time (aPTT), thrombin time (TT), plasma fibrinogen (Fbg).

Laboratory tests should include CBC, blood biochemistry, CRP, coagulation function and urine test during the screening period and the treatment / follow-up observation period (D1, D4, D8 and D15).

Laboratory tests done at Day 1 should be done prior to the infusion.

If the patient clinical status improves and is discharged to home care, the follow up visits can be carried out through telemedicine (phone or video interviews). The laboratory tests, radiology study, ECG and research samples are optional.

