7.1.11. Cytokine and lymphocyte subtype detection (For selected sites only)

If conditions permit, a 5 ml blood sample should be collected and separated into plasma and PBMC. The samples can be frozen and stored for research purposes. Plasma samples are for testing of inflammatory cytokines (IL-1 β , IL-6, TNF- α , MIP α , INF- γ , IP10, MCP, GCSF, IL-10). The PBMC are for testing lymphocyte subtypes and activation/exhaustion markers (flow cytometry detection analysis: CD3 / CD4 / CD8 / PD1 / Tim3, etc.) at D1 before IV infusion, D4, D8 and D15.

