Absolute Lymphocyte Count: patients' dynamic changes in absolute lymphocyte count during the treatment / observation period will be monitored to assess the possible correlation between lymphocyte levels and disease outcome and prognosis.

D-dimer levels: patients' dynamic changes in D-dimer levels during the treatment / observation period will be monitored to assess the possible correlation between lymphocyte levels and disease outcome and prognosis.

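### Section 10.4.3 pairs T-cell depletion with CD4 and CD8 proportions, which understate a change in cell number and can miss it; absolute CD4 and CD8 counts can be derived from data already collected

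*Combined protocol and SAP*

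**What the plan says.** The third exploratory endpoint in Section 2.6 is the effect of the drug on lymphocyte subtype distribution. For its analysis, Section 10.4.3 says the trial will "monitor the dynamic changes of the proportion of CD4 and CD8 T cell subtypes in lymphocytes during the treatment" and "observation period and analyze the state of T cell depletion". The same sentence goes on to mention the lymphocyte level and its possible relation to outcome and prognosis.

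Section 7.1.11 covers the assay: "The PBMC are for testing lymphocyte subtypes and activation/exhaustion markers", by flow cytometry, at selected sites, on D1 before infusion, D4, D8 and D15. Neither section defines an absolute CD4 or CD8 count.

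Absolute lymphocyte count is a secondary endpoint in its own right (Section 2.5). Section 10.4.2 says "patients' dynamic changes in absolute lymphocyte count during the treatment / observation period will be monitored", with the aim of relating it to outcome and prognosis. The blood count in Section 7.1.5 includes lymphocytes and is due at screening, D1 (before infusion), D4, D8 and D15, so it covers every scheduled flow-cytometry visit. No text multiplies the two measurements.

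**The concern.** The stated purpose and the stated measure do not match. Depletion is a fall in the number of T cells. The share of T cells among lymphocytes changes only to the extent that T cells change more than other lymphocytes do.

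The protocol itself treats the matter as one of number. On severe COVID-19, Section 1.2 states: "The reduction of lymphocytes is due to loss of CD4 and CD8 T lymphocyte as B cell numbers are unaffected". Sections 1.3 and 1.13 give protection of T cells from loss as one of the ways the drug is expected to work. If depletion is read from proportions, a real effect on T-cell number would appear smaller than it is and could be missed. What is at stake is the interpretation of a mechanistic endpoint, not the efficacy or safety conclusions.

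**Working it through.** The plan gives no figure for this endpoint, so there is nothing to reproduce. The check is arithmetic on how a share responds to a loss of cells.

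**Inputs.**
- Measure: CD4 and CD8 as a proportion of lymphocytes (Section 10.4.3).
- Pattern of loss: CD4 and CD8 cells lost, B cells unaffected (Section 1.2).
- Assumed, not in the documents: baseline T-cell share f of 0.6 to 0.8, and equal proportional loss of CD4 and CD8. Under equal loss, the CD4 and CD8 shares change by the same relative amount as the T-cell share.

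**Formulas.** Let d be the fraction of T cells lost and e the fraction of other lymphocytes lost.
- Lymphocyte count relative to baseline: L = f(1 − d) + (1 − f)(1 − e)
- T-cell share after loss: s = f(1 − d) / L
- Share relative to baseline: s / f = (1 − d) / L
- Count times share, relative to baseline: L × (1 − d) / L = 1 − d, whatever f and e are

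**Results for a true T-cell loss of 50% (d = 0.5).**

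| f | e | Share after loss | Relative change in share | L | Count × share, relative to baseline |
|---|---|---|---|---|---|
| 0.6 | 0 | 0.30/0.70 = 42.9% | −28.6% | 0.70 | 0.50 |
| 0.7 | 0 | 0.35/0.65 = 53.8% | −23.1% | 0.65 | 0.50 |
| 0.8 | 0 | 0.40/0.60 = 66.7% | −16.7% | 0.60 | 0.50 |
| 0.7 | 0.25 | 0.35/0.575 = 60.9% | −13.0% | 0.575 | 0.50 |
| 0.6 to 0.8 | 0.5 | unchanged | 0% | 0.50 | 0.50 |

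With f = 0.7 and an assumed CD4:CD8 ratio of 2:1, the CD4 share goes from 46.7% to 35.9% when other cells are unaffected, the same 23% relative fall.

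**Rescue is understated too.** If T cells return from half to full number while other cells stay constant, the true change is +100%. The share rises by 60/42.9 − 1 = 40%, 70/53.8 − 1 = 30% or 80/66.7 − 1 = 20% for f = 0.6, 0.7 or 0.8.

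**Lymphocyte count alone does not settle it.** With f = 0.7, a 35% fall in the count (L = 0.65) arises if T cells halve and nothing else changes. It also arises if every type falls by 35%. The T-cell loss is 50% in one case and 35% in the other. Count and share together distinguish them; neither does so alone.

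**Animal data in Section 1.5.** In the spleen, CD4+ T-cell number rose together with total human lymphocytes (Figures 7c and 7d). When numerator and denominator rise together, a share of lymphocytes moves less than the number does. This support is qualitative: the figures are not available and no CD4 share of lymphocytes is reported.

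**The case against.** The strongest reply is that the plan, read as a whole, covers both number and composition. Absolute lymphocyte count is already a secondary endpoint, ranked above this one, and would register a parallel fall in all lymphocytes directly. The sentence in Section 10.4.3 also mentions the lymphocyte level, and does not say that depletion will be judged from the proportion alone. The named endpoint is subtype distribution, for which a proportion is the natural measure, and the exploratory objectives in Section 2.3 do not list depletion. Much of this stands, and it lowers the importance of the point. It does not supply the missing quantity: the total count does not isolate T cells, and mentioning the lymphocyte level does not define a CD4 or CD8 count.

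Two stronger readings are tempting, and the documents support neither.

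- A reader might infer that a proportion cannot show depletion at all. Under the pattern in Section 1.2, with B cells preserved, the planned proportion does fall; it falls too little. The 0% case requires all lymphocyte types to move together, which is not how Section 1.2 describes the disease.
- A reader might take the mouse experiment as proof, because Section 1.5 says "Since the CD4 and CD8 ratio was not altered (Figure 7b), CD24Fc protected against loss of both CD4 and CD8 T cells". Figure 7b, however, reports CD4 as a share of CD3+ T cells in peripheral blood, whereas the cell numbers are from spleen and the trial's planned denominator is lymphocytes. Its constancy shows that CD4 and CD8 moved together. It is not direct evidence about the planned measure.

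It is also fair to say that no false negative can arise in the formal sense, since no test is planned for this endpoint.

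**Conclusion.** The point holds in a limited form. Section 10.4.3 links depletion to a measure that understates changes in T-cell number and can miss them when other lymphocytes move in parallel. For an assumed baseline T-cell share of 60% to 80%, a 50% T-cell loss lowers the share by 29% to 17% if other cells are unchanged, and by 0% if all types halve. The size depends on the assumed share and on what happens to the other lymphocytes; the direction does not, as long as the other cells do not move the opposite way to the T cells.

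The information needed is already scheduled for collection. What is missing is a statement that the two measurements will be combined. Priority is low: the endpoint is exploratory, limited to selected sites and without a formal test, and the primary result is unaffected.

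**What to change.** In Section 10.4.3, state that T-cell depletion will be assessed on absolute CD4 and CD8 counts. Each is the flow-cytometry fraction of lymphocytes multiplied by the lymphocyte count from the same visit's blood count, at D1 before infusion, D4, D8 and D15. Summarise them by arm as change from D1. Keep the proportions as the measure of subtype distribution. Make the change before unblinding, so that the derived variable is not chosen after the results are seen.

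The cost is one derived variable and a sentence or two of text, with no new sample or assay. There are two drawbacks:

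- The product carries the measurement error of both the flow fraction and the blood count.
- Laboratory tests and research samples become optional after discharge (Sections 7.1.5 and 7.1.12), so values will be missing more often in patients who have recovered. Report the number of patients with data at each visit in each arm, and read later visits with that in mind.

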10.4.4. Safety Analysis

Adverse events will be summarized according to the system organ classification (SOC) and preferred term (PT) coded by the MedDra thesaurus. The number of AE, TEAE, SAE, and ADR cases, incidence and number of cases were summarized in each arm.

The results of specific laboratory tests, electrocardiograms, vital signs, and physical examinations will be summarized and their relative baseline changes will be reviewed. Where applicable, the baseline value and the value at each time point after the baseline are presented in the form of a crosstab.

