7.1.8. ECG

During the screening period (up to 72 hr prior to screening is allowed), treatment / follow-up observation period. On the drug administration day (Day 1), ECG should be done before drug infusion and 2 hrs after drug infusion. ECG should be done in visit D8 and D15, if patient is still in hospital.

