7.1.12. Evaluation of clinical status

Clinical status should be evaluated and recorded daily when the patient is hospitalized. The screening period must assess the clinical status and recorded as baseline.

If the patient clinical status improves and is discharged to home care, the follow up visits should follow the study schedule ([Table 2](#)), and the visits can be carried out through telemedicine (phone or video interviews). The clinical investigators should make best effort to obtain the vital signs, clinical status evaluation, concomitant medicines and adverse events assessment. The laboratory tests, radiology study, ECG and research samples are optional.

7.2. **REQUIRED OBSERVATIONS (STUDY CALENDAR as in Synopsis)**

7.2.1. **Screening period**

Visit 1

- Sign the informed consent by patient or by a legally authorized representative;
- Record the past medical history;
- Collect demographic data;
- Record vital signs and physical examination;
- Laboratory tests should be done according to Section 7.1.5. Tests done 72 hrs prior to screening are allowed;
- Record digital oxygen saturation;
- Arterial blood gas analysis (optional, tests done 72 hrs prior to screening are allowed);
- Pregnancy check (women only, under 54 years old);
- ECG. Tests done 72 hrs prior to screening are allowed;
- Chest CT scan or X-ray. Tests done 72 hrs prior to screening are allowed;
- Detection of SARS-CoV-2 viral nucleic acids. Prior positive viral results are allowed;
- Clinical status assessment;
- Collect blood samples for serum cytokines and lymphocyte subtypes (selected sites only);
- Confirm the inclusion / exclusion criteria;
- Record concomitant medications.

7.2.2. **Treatment / follow-up observation period (D1 ~ D29)**

Visit 2 (D1)

- Record vital signs before study drug infusion and at 60±10 minutes after the start of drug infusion;
- Confirm the inclusion / exclusion criteria;
- Subject is randomized;
- Chest CT examination (optional);
- Record digital oxygen saturation;
- Arterial blood gas analysis (optional);

- Laboratory tests according to Section 7.1.5;
- ECG before drug infusion, and at 2 hrs (120 ± 15 min) after drug infusion;
- Study drug administration;
- Clinical status assessment;
- Record IMV / NIV, ECMO, or oxygen therapy;
- Collect blood samples for serum cytokines and lymphocyte subtypes (selected sites only);
- Record adverse events and concomitant medications.

Visit 3 (D4 \pm 2d)

- Record vital signs;
- Clinical status assessment;

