8.2. Adverse Event Reporting

Grade III to V AEs occurring from the time of treatment through the end of study will be documented, recorded, and reported. The Investigator will evaluate Grade III to V AEs with respect to **Severity** (intensity or grade) and **Causality** (relationship to study agent and relationship to research). The investigator will record nonserious adverse events and report them to the sponsor in a timely manner.

Grade III or V laboratory abnormalities that are gradable per the CTCAE v5.0 will be recorded as AEs or SAEs. All other laboratory abnormalities without clinical significance will not be recorded as AEs or SAEs. Grade III to V laboratory abnormalities that require medical or surgical intervention must be recorded as an AE or SAE if applicable. Laboratory assessments that are associated with signs and/or symptoms must be recorded as an AE or SAE if they meet the definition. If a diagnosis is clinically evident, the diagnosis, rather than the individual signs and symptoms or lab abnormalities will be recorded as the AE.

Grade I or II adverse events that worsen to grade III or V during the study will be captured. Their start date will be the day the adverse events worsen to grade III or V.

Events will be summarized on the basis of the date of onset for the event. A treatment-emergent adverse event will be defined as any new or worsening adverse event that begins on or after the date of treatment until study completion. Summaries (number and percentage of subjects) of treatment-emergent adverse events will be provided at study completion.

At each contact with the subject as outlined above in the study activities table, information regarding Grade III or V AEs will be elicited by appropriate questioning and examinations and will be immediately documented in the subject's medical record. Medical records will be reviewed in a timely manner by the research team. The onset date, the end date, the severity of each reportable Grade III to V event, and the Investigator's judgment of the AEs relationship to CD24Fc will also be recorded.

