10. STATISTICAL ANALYSIS

10.1. Sample size

In the phase III trial, the patients will be randomized at 1: 1 ratio into CD24Fc or placebo arms. It was assumed that the time to improvement the clinical status of the patients obeyed the exponential distribution, and the improvement hazard ratio (HR) was 1.54. The median time to improvement in the control group is presumed 11 days, and the median time to improvement in the treatment group is projected as 7.14 days. An interim analysis for efficacy will be performed when 70% of the required events are reached. The O'Brien-Fleming type consumption function of the Lan-DeMets algorithm is used to control the overall class I error rate $\alpha = 0.025$ (one-sided), at least 80% of the degree of confidence. At least 208 events are required to achieve 80% power. Assuming 28 days of patient follow up, the estimated number of 208 events will be reached for the final analysis approximately 28 days after the last subject is enrolled. Assuming 78% recovery rate, 270 participants will be enrolled in this trial.

The sample size was calculated on SAS 9.4 PROC SEQDESIGN.

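### Grade III-V events found only by laboratory test or ECG are reliably looked for only in hospital, yet Section 10.4.4 gives their incidence per arm without the number tested, so the arm discharged sooner may read roughly 5 to 25% lower

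*Combined protocol and SAP*

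**What the plan says.** - **What counts as an event.** Section 8.2 provides that high-grade "laboratory abnormalities that are gradable per the CTCAE v5.0 will be recorded as AEs or SAEs". That sentence names Grades III or V; Section 8.1.6 uses Grades III to V, and I read it that way. Collection runs from Day 1 to Day 29 in both arms (Section 8.1.6).
- **When tests are done.** Section 7.1.5 schedules laboratory tests at screening, D1 (before the infusion), D4, D8 and D15. None is scheduled at D29.
- **After discharge.** Visits may be by telephone or video. Section 7.1.12 then says "The laboratory tests, radiology study, ECG and research samples are optional". Footnote 7 of the study schedule (Table 2) is a little firmer: it recommends the scheduled laboratory studies without making them mandatory. For ECG, Section 7.1.8 says "ECG should be done in visit D8 and D15, if patient is still in hospital". Every dosed patient is also scheduled for an ECG 2 hours after the infusion.
- **How events are summarised.** Section 10.4.4: "The number of AE, TEAE, SAE, and ADR cases, incidence and number of cases were summarized in each arm". Its second paragraph adds summaries of laboratory and ECG results, with baseline cross-tabulated against later time points. Neither paragraph mentions the number tested, time under observation, or how to treat tests not done after discharge.

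**The concern.** A telephone visit can elicit symptoms. It cannot detect a symptomless Grade III laboratory value or a silent rhythm change. For events found only by test, the chance of detection depends on still being in hospital, and that is an outcome the treatment is expected to change. A per-arm incidence with no matching number tested then mixes true risk with opportunity to detect, and the error favours the arm that goes home sooner.

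Safety is part of the primary objective (Section 2.1), and the earlier drug-related signals were partly of this kind: ventricular tachycardia in Phase I (Section 1.8.1) and Grade 3/4/5 hyperglycaemia at 480 mg in Phase IIa (Section 1.8.2). The mean half-life at 480 mg was 406.648 hours (Section 1.9.2), about 17 days, so exposure continues after many faster-recovering patients may have stopped being tested.

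**Working it through.** **Inputs from Section 10.1.** "The median time to improvement in the control group is presumed 11 days"; "the median time to improvement in the treatment group is projected as 7.14 days"; "the improvement hazard ratio (HR) was 1.54"; exponential times. Check of the plan's own figure: 11 / 1.54 = 7.14 days, which reproduces.

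**Assumptions that the documents do not give.** Discharge follows improvement by a fixed lag L (0 to 6 days), because scale 5 and 6 patients are still in hospital (Appendix A). No tests are done after discharge, unless a share u is stated. The underlying event hazard is the same in both arms, in and out of hospital. Deaths are ignored.

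**Step 1: scheduled tests per patient.** With λ = ln 2 / median, λ is 0.0630 (placebo) and 0.0971 (CD24Fc) per day. D4, D8 and D15 fall 3, 7 and 14 days after D1. The probability of being in hospital at day t is exp(−λ·max(0, t − L)).

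- L = 0, placebo: 0.828 + 0.643 + 0.414 = 1.88. CD24Fc: 0.747 + 0.507 + 0.257 = 1.51. That is 19.8% fewer.
- L = 2: 2.14 and 1.83, 14.2% fewer.
- L = 4: 2.36 and 2.13, 9.9% fewer.
- D8 and D15 ECGs, L = 0: 1.06 and 0.76, 27.8% fewer; 14.3% fewer if the 2-hour ECG on Day 1 is counted.

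**Step 2: observable days.** Mean days in hospital up to τ = L + (1 − exp(−λ(τ − L)))/λ. With L = 0 this is 9.30 and 7.65 days for τ = 14 (17.7% fewer), and 13.15 and 9.62 days for τ = 28 (26.8% fewer). The 14-day window fits scheduled tests. The 28-day window matters only for unscheduled testing during ward care, whose frequency is not given.

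**Step 3: effect on crude incidence.** With constant hazard h, the probability that an event is seen is h/(h + λ) × (1 − exp(−(h + λ)τ)). For an assumed true 14-day risk of 20%, it is 13.5% on placebo and 11.2% on CD24Fc, a ratio of 0.83. With 135 per arm, that is about 18 and 15 patients, with no true difference.

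**Step 4: sensitivity.** Apparent reduction on CD24Fc:

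| Assumption changed | To D15 | To 28 days |
|---|---|---|
| None (L = 0, u = 0, constant hazard) | 17.7% | 26.8% |
| L = 2, 4, 6 days | 12.8, 8.9, 5.9% | 22.4, 18.8, 15.7% |
| u = 25%, 50% | 11.8, 7.1% | 15.7, 8.6% |
| Hazard falling, half-life 2 to 7 days | 7.6 to 13.8% | 7.7 to 16.8% |
| Rates set to the plan's 78% recovery | 13.5% | 22.1% |
| L = 6 and u = 50% | 2.7% | 6.1% |

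The 78% row is there because the plan's medians imply 82.9% and 93.4% improved by day 28, an average of 88%. Across all the checks the range is about 3 to 28%; 5 to 25% is a rounded working range without the extremes.

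**Step 5: would a rate per in-hospital day cure it?** Only if the hazard is constant. If the hazard falls with a 3-day half-life, events seen over 28 days are 10.4% fewer on CD24Fc (ratio 0.896), while in-hospital days have ratio 9.62 / 13.15 = 0.732. The rate ratio is 0.896 / 0.732 = 1.22, which wrongly makes CD24Fc look worse.

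**The case against.** A reader might infer that laboratory and ECG events can be seen only in hospital, across the whole 28 days, so that CD24Fc would look 15 to 25% safer with no true difference. The documents do not support that, for four reasons.

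- Tests after discharge are optional or recommended, not excluded, and Section 8.1.6 speaks of laboratory assays at each visit for all dosed patients.
- Scheduled laboratory tests and ECGs stop at D15 in both arms. On scheduled laboratory sets the deficit is 10 to 20%.
- Only test-detected events are affected. Other Grade III-V events are sought to D29, by telephone or video if need be. Section 8.1.2 defines serious events as death, life-threatening events needing intensive care, or organ failure, and the stopping guideline rests on serious events. Section 8.2 also records an evident diagnosis in place of the laboratory value.
- Calling the shortfall pure artefact requires that patients at home keep the same daily risk as inpatients. If risk falls with recovery, part of a lower incidence would be real. It is therefore not established that a true laboratory toxicity of similar size would be hidden.

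It is also fair to say that the comparison is descriptive, that events close to dosing occur while all patients are in hospital, and that the cross-tabulation in Section 10.4.4 comes near to a by-visit display. These points limit the size of the problem but do not remove it. The cross-tabulation does not state the number tested by arm and does not correct the adverse event incidence.

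**Conclusion.** The point holds for Grade III-V events detected only by laboratory test or ECG. Their ascertainment depends on hospital stay, the plan gives no number tested, and crude incidence may read lower in the arm discharged sooner. The direction follows from the text if CD24Fc shortens hospital stay as the plan's improvement times suggest. The size, roughly 5 to 25%, rests on discharge lag, uptake of testing after discharge and event timing, all of which are assumptions here. It should not be read as a statement about overall safety: if such events were 25 to 50% of all adverse events (also an assumption), the effect on the total would be about 4 to 13% even with no lag and no testing after discharge. This is worth correcting because the correction is cheap, not because the safety conclusions would otherwise fail.

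**What to change.** In Section 10.4.4, or in the detailed analysis plan to which Section 10.3.1 points:

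1. Keep crude incidence, but report laboratory- and ECG-detected Grade III-V events separately from clinically reported ones.
2. By arm, give the number of patients with a new Grade III or higher laboratory value over the number actually tested at D4, D8 and D15. Do the same for new ECG abnormalities at D8 and D15.
3. State that crude incidence of these events is not comparable between arms if the numbers tested differ.
4. Do not make events per in-hospital patient-day the main comparison. After a single Day 1 dose, early events divided by a shorter stay count against the faster-recovering arm (Step 5 of the working).

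The cost is some wording and one extra table from data already collected; patient management does not change. The limitation is that patients still being tested are a sicker selection, and more so in the arm that recovers faster. The by-visit proportions need that note beside them and do not estimate risk in all dosed patients.
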